5.2.3.2 Concomitant Therapy

All medications (including, but not limited to, prescription or over-the-counter medicines such as aspirin, antacids, vitamins, mineral supplements, and herbal preparations) that the subject is receiving from Baseline through the end of the study, must be recorded on the appropriate electronic Case Report Form (eCRF) along with the reason for use, dates of administration including start and end dates, and dosage including dose, frequency and route of administration.

Subjects will be allowed two periocular corticosteroid injections per eye per year during the duration of the study at the investigator's discretion. No intraocular or intravitreal injections will be allowed.

Subjects will be allowed to continue on one ongoing non-biologic protocol-permitted immunosuppressive therapy and one systemic corticosteroid at study entry. Alternatively, if the subject has not been on a non-biologic immunosuppressive previously, they can add one of the following at any time during the Study M11-327. In addition, doses must be within the acceptable limits listed below:

- Methotrexate (MTX) \leq 25 mg per week

- Cyclosporine \leq 4 mg/kg per day
- Mycophenolate mofetil \leq 2 grams per day or an equivalent drug to mycophenolate mofetil (e.g., mycophenolic acid) at an equivalent dose approved by the Medical Monitor
- Azathioprine \leq 175 mg per day
- Tacrolimus (oral formulation) \leq 8 mg per day

The non-biologic immunosuppressive drug and/or corticosteroids can be initiated, changed or discontinued during the course of the study if it is considered appropriate for the subject in the investigator's expert opinion.

Dosage of topical eye drops (including topical corticosteroid eye drops) may be initiated or adjusted as medically necessary during the study.

The initiation, discontinuation and/or changes in dosing of these non-biologic immunosuppressive therapies and corticosteroids can have an impact on uveitis. However, the intent of allowing these to occur, is to reflect standard clinical practice in the management of uveitis.

Each vaccine administered to the subject should be listed as a concomitant medication on the Other Medications eCRF. Live vaccines may not be given concurrently while on study drug or for 70 days after the last dose of adalimumab.

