## **7.5 Concomitant Medications**

Medications with a start date prior to or on the first dose of adalimumab in Study M11-327 and a stop date on or after the first dose of adalimumab in Study M11-327 or a missing stop date will be considered as concomitant medications at baseline of Study M11-327. If the start date is missing and the stop date is on or after the baseline date in Study M11-327, or if start and stop dates are both missing, the medication will also be considered as concomitant at baseline in Study M11-327. The following therapies used by subjects at baseline in Study M11-327 will be summarized by counts and percentages:

- Immunosuppressants (IMMs)
  - Azathioprine

- Cyclosporine
- Methotrexate (MTX)
- Mycophenolate mofetil or equivalent drug (e.g. mycophenolic acid)
- Tacrolimus
- Corticosteroids (CSs)
  - Oral corticosteroids
  - Topical corticosteroids
  - Other corticosteroids

Concomitant medication is defined as any medication that started prior to the first dose of adalimumab in Study M11-327 and continued to be taken after the first dose of adalimumab in Study M11-327 or any medication that started after the first dose of adalimumab in Study M11-327, but not after the last dose of adalimumab in Study M11-327. The number and percentage of subjects who had taken concomitant medications will be summarized by generic drug name based on the World Health Organization (WHO) drug dictionary.

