### **10.2 Efficacy Variables**

The following efficacy variables will be analyzed:

- Proportion of subjects with no active lesions in both eyes at each study time point.
- Proportion of subjects at each study time point with no new active, inflammatory chorioretinal or inflammatory retinal vascular lesion in both eyes relative to Baseline for subjects who had inactive uveitis when they entered the study and to Week 8 for subjects who had active uveitis when they entered the study.
- AC cell grade left/right eye and mean of both eyes at each study time point.
- Proportion of subjects at each study time point with a Grade  $\leq 0.5+$  in AC cells in both eyes on Slit Lamp Exam, according to SUN criteria.

- VH grades left/right eye and mean of both eyes at each study time point.
- Proportion of subjects at each study time point with a Grade  $\leq 0.5+$  in vitreous haze in both eyes on indirect ophthalmoscopy, according to NEI/SUN criteria.
- Proportion of subjects at each study time point with VH  $\leq 0.5$  and AC  $\leq 0.5$ .
- Proportion of subjects at each study time point with new lesions, AC  $\geq 2$  or VH  $\geq 2$ .
- Proportion of subjects at each study time point in quiescence defined as no active lesions, AC  $\leq 0.5$  and VH  $\leq 0.5$ .
- Proportion of subjects who experienced a uveitis flare (defined as no quiescence) during the study and who did or did not discontinue from the study due to the flare.
- LogMAR Best corrected visual acuity (BCVA) left/right eye and mean of both eyes at each study time point.
- Proportion of subjects at each study time point without a worsening of BCVA by  $\geq 15$  letters on the Early Treatment Diabetic Retinopathy Study (ETDRS) in both eyes relative to Baseline for subjects who had inactive uveitis when they entered the study and to Week 8 for subjects who had active uveitis when they entered the study.
- Proportion of subjects who started IMMs in Study M11-327.
- Proportion of subjects on/off IMMs at each study time point only in subjects on IMMs at baseline of Study M11-327.
- Proportion of subjects at each study time point achieving a  $\geq 50\%$  reduction in immunosuppression load relative to Baseline for subjects who had inactive uveitis when they entered the study and to Week 8 for subjects who had active uveitis when they entered the study.

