Immunosuppression load will be assessed according to the article by Nussenblatt et al. (2005). The below grading scheme will be used to accommodate the simultaneous use of multiple agents and provide a combined, single numeric score for the total immunosuppression load per unit body weight per day at each visit. For patients receiving multiple medications, the sum of the grading scores for each drug will be used to calculate a total immunosuppression score at each visit.

Medication	Immunosuppression Grade Based on Dose in mg/kg/day (or per Week if Dosed Weekly)							
	0	1	2	3	4	5	6	7
Prednisone	0	< 0.15	0.15 – 0.30	0.31 – 0.45	0.46 – 0.60	0.61 – 0.75	0.76 – 0.90	0.91 – 1.05
Cyclosporine	0	< 0.75	0.75 – 1.50	1.51 – 2.25	2.26 – 3.00	3.01 – 3.75	3.76 – 4.50	4.51 – 5.25
Azathioprine	0	< 0.25	0.25 – 0.50	0.51 – 0.75	0.76 – 1.00	1.01 – 1.25	1.26 – 1.50	1.51 – 1.75
Mycophenolate	0	< 10	10 – 20	21 – 30	31 – 40	41 – 50	51 – 60	> 60
Methotrexate	0	< 0.05	0.05 – 0.10	0.11 – 0.15	0.16 – 0.20	0.21 – 0.25	0.26 – 0.30	0.31 – 0.35
Cyclophosphamide	0	< 0.25	0.25 – 0.50	0.51 – 0.75	0.76 – 1.00	1.01 – 1.25	1.26 – 1.50	1.51 – 1.75
Chlorambucil	0	< 0.025	0.025 – 0.050	0.051 – 0.075	0.076 – 0.100	0.101 – 0.125	0.126 – 0.150	0.151 – 0.175

Note: Dose ranges are for the average in mg/kg/day, except for weekly doses of methotrexate, which are measured as mg/kg/week

The efficacy variables will be analyzed as follows.

Descriptive statistics for quantitative variables will include the number of observations, mean, standard deviation, minimum, first quartile, median, third quartile, and maximum for values at each visit, changes from Baseline/Week 8 to each visit thereafter and change from Baseline/Week 8 to Final/Early Termination Visit for continuous variables. In addition, for central retinal thickness percent change from Baseline/Week 8 to each visit thereafter and percent change from Baseline/Week 8 to Final/Early Termination Visit will be analyzed. For central retinal thickness, values at each visit and changes will be analyzed by OCT machine, percent changes will be analyzed overall. 95% confidence intervals for means will be provided. Data will be analyzed by Last Observation Carried Forward (LOCF) and as observed. For as observed analyses, graphs will be generated for subjects with active vs. inactive uveitis at entry of Study M11-327 for:

- LogMAR Best corrected visual acuity (BCVA) (mean of both eyes) at each study time point.

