### **Subgroup Analyses of Adverse Events**

Analyses of AEs per subgroup will be presented for the AE overview. The number and percentage of subjects experiencing AEs as well as E/100PYs will be tabulated overall.

Subgroups used for the analyses are:

- Concomitant use of corticosteroids (yes, no)
- Baseline immunosuppressant usage (yes, no)
- Baseline azathioprine usage
- Baseline cyclosporine usage
- Baseline methotrexate usage

- Baseline mycophenolate mofetil or an equivalent drug (e.g., mycophenolic acid) usage
- Baseline tacrolimus usage

An AE overview (with number and percentage of subjects experiencing treatment-emergent AEs as well as E/100PYs) will also be presented separately for

- treatment periods with/without concomitant use of corticosteroids
- treatment periods with corticosteroid dose  $> 0$  to  $\leq 15$  mg/day
- treatment periods with corticosteroid dose  $> 15$  mg/day
- treatment periods with/without concomitant use of immunosuppressant
- treatment periods
  - without concomitant use of corticosteroids and immunosuppressant
  - with concomitant use of corticosteroids only
  - with concomitant use of immunosuppressant only
  - with concomitant use of corticosteroids and immunosuppressant

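### The immunosuppression-load score has no grade for tacrolimus and no rule for a zero reference load, so the ≥50% reduction proportion can be distorted or depend on programming

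*SAP*

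**What the plan says.** **Endpoint.** The proportion of subjects whose immunosuppression load has at least halved is one of the seven efficacy variables in Protocol 5.3.3. SAP 10.2 keeps it as a "reduction in immunosuppression load relative to Baseline for subjects who had inactive uveitis when they entered the study", with Week 8 as the reference for those who entered with active disease.

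**Scoring.** SAP 10.2 states: "Immunosuppression load will be assessed according to the article" that it cites, and then prints the table to be used. Its rows are prednisone, cyclosporine, azathioprine, mycophenolate, methotrexate, cyclophosphamide and chlorambucil, each graded 0 to 7 by dose per kg. For several drugs, "the sum of the grading scores for each drug will be used to calculate a total immunosuppression score at each visit". No rule is given for a drug without a row.

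**Permitted drugs.** Protocol 5.2.3.2 lists oral tacrolimus among five permitted immunosuppressants. Of subjects with no previous non-biologic immunosuppressant it says "they can add one of the following at any time during the Study M11-327". It adds: "The non-biologic immunosuppressive drug and/or corticosteroids can be initiated, changed or discontinued during the course of the study". Protocol 5.1 allows one such drug at a time beside a systemic corticosteroid. Protocol 5.2.3.3 prohibits cyclophosphamide and chlorambucil.

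**Tacrolimus elsewhere in the SAP.** Section 7.5 says "The following therapies used by subjects at baseline in Study M11-327 will be summarized by counts and percentages", and tacrolimus is on the list that follows. Section 11.1 plans an adverse-event subgroup: "Baseline tacrolimus usage".

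**Population and missing data.** Efficacy uses the ITT set, whose definition (SAP 5.1) does not refer to load. Binary variables are analysed by NRI, where missing means non-response (SAP 6.3.1), and as observed, where missing values are left out (SAP 6.3.3). The neighbouring SAP 10.2 variables on being on or off immunosuppressants, change in immunosuppressant dose and percent change in corticosteroid dose are limited to users at the reference visit. The load variable is not.

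**The concern.** The score is meant to measure how much immunosuppression a subject still needs. With tacrolimus ungraded, replacing one immunosuppressant by another can look like a reduction. The reverse also holds: a subject who stops tacrolimus gets no credit, and one who takes it alone appears to be on nothing.

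Separately, a subject with load 0 at the reference visit cannot reduce it. Keeping such subjects in the denominator mixes the response rate with the share who had nothing to reduce. Leaving their coding unstated lets the result depend on how a zero divided by zero is programmed.

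The proportion is reported at every visit with a 95% confidence interval. Readers may well set it beside the earlier prospective study described in Protocol 3.5.2, where 111 of 131 patients (85%) reduced load by at least half.

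**Working it through.** The plan states no expected value for this proportion, so there is no figure to reproduce. The check applies the SAP table as printed. Body weight, doses and rates below are assumptions, since the documents give no distribution of weight, dose, tacrolimus use or zero load. Doses are rounded to the table's two decimals.

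**1. Switch to tacrolimus.** With prednisone grade p unchanged and one immunosuppressant of grade m replaced by tacrolimus (0), load goes from p + m to p. The reduction is m/(p + m), which is at least 50% exactly when m ≥ p.

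| At 70 kg, before the switch | Grades | Load | Reduction |
|---|---|---|---|
| Prednisone 5 mg/day (0.07 mg/kg), cyclosporine 3.00 mg/kg/day | 1 + 4 | 5 to 1 | 80% |
| Prednisone 5 mg/day, methotrexate 15 mg/week (0.21 mg/kg) | 1 + 5 | 6 to 1 | 83% |
| Prednisone 30 mg/day (0.43), methotrexate 10 mg/week (0.14) | 3 + 3 | 6 to 3 | 50% |
| Prednisone 40 mg/day (0.57), methotrexate 10 mg/week | 4 + 3 | 7 to 4 | 43%, no response |

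Over all pairs with p from 0 to 7 and m from 1 to 7, the switch is a response in 7+7+6+5+4+3+2+1 = 35 of 56. With p at most 2 it is 20 of 21. These count grade pairs, not subjects.

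**2. Adding or stopping tacrolimus.**
- Prednisone cut from 20 to 10 mg/day with tacrolimus added, 70 kg: 0.29 to 0.14 mg/kg, grade 2 to 1, a 50% reduction and a response. At 60 kg the same change is 0.33 to 0.17, grade 3 to 2, 33% and no response.
- Tacrolimus with prednisone 5 mg/day at the reference visit: stopping tacrolimus gives 1 to 1 (0%); stopping only prednisone gives 1 to 0 (100%).
- Tacrolimus alone scores 0, so stopping it can never show as a reduction.

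**3. Zero reference load.** Let z be the share with load 0 at Baseline/Week 8 and r the response rate among the rest, ignoring other missing data.
- Read plainly as not achieving a reduction, or set to missing under NRI: r(1 − z).
- Set to missing, as observed: r.
- Coded as current load ≤ half the reference, with load still 0 (0 ≤ 0 is true): r(1 − z) + z.

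| z | r = 40% | r = 60% |
|---|---|---|
| 10% | 36 / 40 / 46% | 54 / 60 / 64% |
| 25% | 30 / 40 / 55% | 45 / 60 / 70% |
| 50% | 20 / 40 / 70% | 30 / 60 / 80% |

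With the protocol's estimated 400 subjects, the denominator limited to load above zero would be 360, 300 or 200.

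**The case against.** **The cited article may supply the missing rules.** It was not available for this check. But the SAP says that the printed table is the scheme to be used. If the article has a rule for tacrolimus, the SAP needs to state it.

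**The user-only neighbours are a weak comparison.** The load variable comes from the protocol, while those neighbours were added in SAP Amendment 2. Different wording may reflect different origins, and a narrower denominator changes a proportion that the protocol states for all subjects. That is fair, and it is why the all-subject version should stay as a sensitivity analysis. It does not settle how a zero load is coded.

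**Impact is limited.** All analyses are descriptive, load is neither graphed nor among the SAP 10.4 subgroup variables, and SAP 10.2 separately reports immunosuppressant starts, on/off use, dose changes, corticosteroid dose and steroid-free quiescence without this score. Listing tacrolimus does not show that anyone took it. All of this stands and limits the weight of the point.

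**Stronger readings that the documents do not support.**
- That every switch to tacrolimus is a response: the fourth example in the working is not.
- That zero-load subjects are always non-responders: no coding is stated, and set to missing they leave the as-observed analysis.
- That the overstatement cannot exceed the share newly on tacrolimus: a subject on it at the reference visit who stops only prednisone scores a 100% reduction.
- That the closed top ends of the azathioprine and methotrexate rows are a further fault, or that capping at grade 7 is merely conservative: the article may cover this, and the direction is not fixed. At 60 kg, azathioprine 150 mg/day unchanged with prednisone 60 mg/day stopped is 14 to 7 (50%) capped, but 17 to 10 (41%) with grades extended in the same steps.

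**Conclusion.** The concern holds in a limited form. The score omits a permitted drug that the SAP itself treats as an immunosuppressant, and on the plain reading that drug counts as zero. A switch to it is then a response whenever the replaced drug's grade is at least the sum of the remaining grades. The denominator sets no condition on reference load, so the reported proportion is diluted or depends on coding: 45%, 60% or 70% in the illustration with z = 25% and r = 60%.

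The tacrolimus results assume that it is scored 0; the zero-load figures rest on assumed values of z and r. The documents do not show how many subjects are affected, or whether the net error is upward or downward. The main safety conclusions are untouched. The SAP should be changed because this is a protocol-listed endpoint and the remedy is cheap.

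**What to change.** Amend SAP 10.2, for scoring only and with no change to treatment.

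1. Limit the main ≥50% reduction denominator to subjects with load above zero at Baseline/Week 8. Report the number with zero load, and show the all-subject denominator, with its coding stated, as a sensitivity analysis.
2. Do not let tacrolimus score zero. Either pre-specify a sponsor-chosen tacrolimus grade, or do not count a subject newly on tacrolimus as a responder at that visit and summarise those on it at the reference visit separately. Show the literal table as a sensitivity analysis.
3. Apply the tacrolimus rule before identifying zero-load subjects, so that someone on tacrolimus alone is not counted as having no load.

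The cost is SAP text and reprogramming of one variable, with no new data. The main denominator becomes smaller, and the tacrolimus rule is a convention outside the cited scheme that may deny some genuine reductions.

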### **10.3 Other Efficacy Variables**

The following other efficacy variables will be analyzed:

- Work Productivity and Activity Impairment, Questionnaire: Specific Health Problem Questionnaire (WPAI:SHP) and its components
- EuroQol Questionnaire (EQ-5D)
- Health Resource Utilization Questionnaire (HRU)

These other efficacy variables will be analyzed as follows.

For WPAI: SHP and EQ-5D, descriptive statistics will include the number of observations, mean, standard deviation, minimum, first quartile, median, third quartile, and maximum for values at each visit, changes from Baseline/Week 8 to each visit thereafter and change from Baseline/Week 8 to Final/Early Termination Visit for continuous variables. Data will be analyzed by Last Observation Carried Forward (LOCF) and as observed.

For HRU data, the individual cumulative number of utilizations per time under observation in Study M11-327 will be calculated in each category (i.e., unscheduled uveitis-related health care professional visits, emergency room visits, hospital admissions and the total number of days in hospital) as follows:

- Time under observation for a subject will be defined as "date of last visit with non-missing HRU – date of Baseline/Week 8 for subjects with inactive/active uveitis."
- The number of utilizations (documented starting at Week 2/Week 12 for subjects with inactive/active uveitis) will be summed up for each subject.

For cumulative HRU data, the ratio of the total number of utilizations (i.e., separately over all subjects with inactive and active uveitis) and the total time under observation (i.e., separately over all subjects with inactive and active uveitis) will be calculated across all subjects. HRU will be analyzed as observed only.

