Subjects may be on only one of the allowed systemic immunosuppressants in addition to a systemic corticosteroid, at any timepoint.

Study visits will occur at Week 0, 2, 4, 8, 12, 18 and every 12 weeks thereafter. Efficacy assessments will be performed at every visit (Section 5.3.1). Both of the subject's eyes should be evaluated. **There will be no designated "study eye."**

Subjects who enter the study due to Treatment Failure in Study M10-877 or Study M10-880 and fail to achieve adequate control of their disease flare within the first 8 weeks may discontinue from the study.

Any other subject experiencing a uveitis flare during the study as determined by the investigator may discontinue from the study. Subjects may continue in the study, if it is determined by the investigator that the flare was triggered by a reduction or discontinuation in concomitant corticosteroid or systemic immunosuppressive therapy where further adjustment to the concomitant therapy may be warranted. Any subject continuing to have an active uveitis flare for 4 weeks or more should be discontinued from the study.

The site research staff will instruct and supervise subjects or a designee on proper injection technique at the scheduled visits. Subjects or a trained designee will administer adalimumab outside of clinic visits according to the specified dosing schedule.

An Independent Data Monitoring Committee (IDMC) will be established to independently monitor and assess data for Study M10-877, Study M10-880 and Study M11-327. The IDMC will be in effect until the end of both Study M10-877 and Study M10-880. At each committee meeting, the IDMC will undertake a comprehensive review and assessment of the cumulative safety data, which will include M11-327 study data.

Subjects may discontinue adalimumab treatment at any time during study participation. Subjects that end study participation early will have an Early Termination Visit. No study drug will be administered or injected at the final visit.

Safety data will be collected in the form of adverse events, physical examination, vital signs and laboratory tests throughout the treatment period and up to 70 days after the last injection in this study. All subjects will have a 70-day follow-up phone call or clinic visit to obtain follow-up information on any new or ongoing adverse events. The 70-day follow-up phone call will not be required for any subject that initiates commercial adalimumab after the end of study participation.

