The VFQ-25 will be completed at the Baseline visit (or as part of the Final/Early Termination visit of Study M10-877 or Study M10-880), Week 8, Week 18 and every visit thereafter prior to any study procedure or examination. A copy of the questionnaire is located in Appendix G.

The questionnaire will be interview administered. The site will complete this questionnaire directly onto the CRFs and will be considered source documents.

EuroQol-5D Questionnaire (EQ-5D)

Subjects will complete the EQ-5D questionnaire at the Baseline visit (or as part of the Final/Early Termination visit of Study M10-877 or Study M10-880), Week 8, Week 18 and every visit thereafter prior to any study procedure or examination. A copy of the questionnaire is located in Appendix H. The subject will complete this questionnaire directly onto the CRFs and will be considered source documents.

Site staff should complete the questionnaire with the subject, if the subject has impaired vision that precludes him/her from reading and completing the questionnaire.

Work Productivity and Activity Impairment, Questionnaire: Specific Health Problem Questionnaire (WPAI-SHP)

Subjects will complete the WPAI-SHP questionnaire at the Baseline visit (or as part of the Final/Early Termination visit of Study M10-877 or Study M10-880), Week 8, Week 18

and every visit thereafter prior to any study procedure or examination. A copy of the questionnaire is located in Appendix J. The subject will complete this questionnaire directly onto the CRFs and will be considered source documents.

Site staff should complete the questionnaire with the subject, if the subject has impaired vision that precludes him/her from reading and completing the questionnaire.

Health Resource Utilization Questionnaire (HRU)

Sites will complete the HRU questionnaire at the Baseline visit (or as part of the Final/Early Termination visit of Study M10-877 or Study M10-880), and at all subsequent visits in the study. A copy of the questionnaire is located in Appendix I.

The questionnaire will be interview administered by the site. The answers will be documented on the source worksheet provided by the sponsor and entered in the eCRF.

Vital Signs/Weight/Height

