Appendix I. Health Resource Utilization Questionnaire (HRU)

Since the last study visit has the subject had any visits for their uveitis other than the protocol required visit?

YES: _____

NO: _____

If YES, please provide the following:

1. Since the last protocol required visit, has the subject been seen by a health care professional for their uveitis?

YES: _____

NO: _____

If YES, how many times: _____

2. Since the last protocol required visit, has the subject been seen in the Emergency Room for their uveitis?

YES: _____

NO: _____

If YES, how many times: _____

3. Since the last protocol required visit, has the subject been admitted to the hospital due to their uveitis?

YES: _____

NO: _____

If YES, please list the ADMISSION DATE: _____/_____/_____
DD MMM YYYY

DISCHARGE DATE: _____/_____/_____
DD MMM YYYY

**Appendix J. Work Productivity and Activity Impairment, Questionnaire:
Specific Health Problem Questionnaire V2.0 (WPAI-SHP)**

The following questions ask about the effect of your UVEITIS on your ability to work and perform regular activities. *Please fill in the blanks or circle a number, as indicated.*

1. Are you currently employed (working for pay)? _____ NO ___ YES
If NO, check "NO" and skip to question 6.

The next questions are about the **past 7 days**, not including today.

2. During the past 7 days, how many hours did you miss from work because of problems associated with your UVEITIS? Include hours you missed on sick days, times you went in late, left early, etc., because of your UVEITIS. Do not include time you missed to participate in this study.

_____ HOURS

3. During the past seven days, how many hours did you miss from work because of any other reason, such as vacation, holidays, time off to participate in this study?

_____ HOURS

4. During the past seven days, how many hours did you actually work?

_____ HOURS (*If "0," skip to question 6.*)

5. During the past 7 days, how much did your UVEITIS affect your productivity while you were working?

Think about days you were limited in the amount or kind of work you could do, days you accomplished less than you would like, or days you could not do your work as carefully as usual. If UVEITIS affected your work only a little, choose a low number. Choose a high number if UVEITIS affected your work a great deal.

Consider only how much UVEITIS affected productivity while you were working.

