## **7.0                    Demographics, Baseline Characteristics, Medical History, and Previous/Concomitant Medications**

The subsequently described analyses will be provided by active uveitis (defined as having discontinued the parent study, Study M10-877/M10-880 due to Treatment Failure) versus inactive uveitis and overall in the ITT set.

All statistical analyses will be descriptive. Descriptive statistics will include the number of observations, mean, standard deviation, minimum, first quartile, median, third quartile, and maximum for continuous variables; and counts and percentages for discrete variables.

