## **10.0 Efficacy Analysis**

### **10.1 General Considerations**

The subsequently described analyses will be provided in the ITT set. All statistical analyses will be descriptive. Results will be stratified between subjects who entered into the study with active versus inactive uveitis. For subjects who had inactive and subjects who had active uveitis when they entered the study, the efficacy analyses will start at Baseline of Study M11-327. Results will also be provided overall except for efficacy variables defined differently for subjects entering Study M11-327 with active and inactive uveitis.

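### For active-entry subjects the HRU rate starts at Week 8, so it is conditional on remaining past Week 8 and not comparable with the inactive-entry rate counted from Baseline

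*SAP*

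**What the plan says.** SAP 10.3 forms the HRU rate as total utilisations over total time under observation, separately for subjects who entered with inactive and active uveitis. Time is defined as "date of last visit with non-missing HRU – date of Baseline/Week 8 for subjects with inactive/active uveitis". For the numerator, "The number of utilizations (documented starting at Week 2/Week 12 for subjects with inactive/active uveitis) will be summed up for each subject". No imputation is planned: "HRU will be analyzed as observed only". The SAP defines no other HRU summary.

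SAP 7.0 defines active entry as having left the parent study for Treatment Failure. Protocol 5.1 says these subjects have active disease on entry, and that those who "fail to achieve adequate control of their disease flare within the first 8 weeks may discontinue from the study".

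Protocol 5.3.1.1 has the HRU completed at Baseline "and at all subsequent visits in the study". Table 1 marks it at Baseline, Week 4, Week 8 and onward, but not at Week 2. The form in Appendix I asks about the interval between visits: "Since the last protocol required visit, has the subject been seen by a health care professional for their uveitis".

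Protocol 8.1.4 starts the efficacy analyses at Week 8 for active entry and Week 0 for inactive entry. SAP 10.1, as amended, says for both groups that "the efficacy analyses will start at Baseline of Study M11-327". The list of changes for that SAP amendment covers 10.1, 10.2 and 10.4, but not 10.3.

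**The concern.** SAP 10.3 presents the HRU figure as cumulative use over time under observation in this study, across all subjects of the stratum. For active entrants it is neither. It describes use after Week 8 among those still in the study then. The part left out is the period straight after treatment failure, and the subjects left out include those whose flare was not controlled.

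A change score needs a reference visit, so a Week 8 reference for active entrants has a function in SAP 10.2. A count over time needs no reference value; here Week 8 only truncates data already collected. The two strata are then printed on different time origins, and a reader who sets the two rates side by side is comparing different phases of treatment.

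**Working it through.** The plan gives no HRU rate, no early-exit share and no mean follow-up, so there is no figure to reproduce.

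**Step 1: what each form covers.** The recall period is the time since the last protocol-required visit. The Week 12 form therefore covers Weeks 8–12 and the Week 8 form covers Weeks 4–8. Starting the count at Week 12 and the clock at Week 8 is internally matched, and it removes everything before Week 8.

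**Step 2: subjects who leave by Week 8.** They have no form from Week 12 on, so they add nothing to the numerator. For the denominator, SAP 6.2 gives nominal days 29 (Week 4) and 57 (Week 8). A last HRU at Week 4 gives 29 − 57 = −28 days if the nominal Week 8 day is used, and an undefined time if there is no Week 8 date. SAP 10.3 gives no rule for either case.

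**Step 3: reported rate against the from-Baseline rate.** Let R be the rate in Weeks 0–8 divided by the rate afterwards, and D the mean follow-up in weeks from Baseline. Both are assumed. For subjects who stay,

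reported / from-Baseline = D / (8R + D − 8).

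Example: R = 2, D = 52 gives 52 / (16 + 44) = 0.867, or 13% below.

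| R | D = 52 | D = 104 | D = 156 |
|---|---|---|---|
| 0.5 | 8% above | 4% above | 3% above |
| 1 | equal | equal | equal |
| 2 | 13% below | 7% below | 5% below |
| 3 | 24% below | 13% below | 9% below |
| 5 | 38% below | 24% below | 17% below |

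**Step 4: what early leavers add.** Let a share d leave by Week 8 after a mean of 6 weeks (assumed), with the same raised early rate, and let D be the follow-up of those who stay. Then

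from-Baseline / reported = [6dR + (1 − d)(8R + D − 8)] / [6d + (1 − d)D].

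With d = 10%, R = 3, D = 52: (1.8 + 61.2) / (0.6 + 46.8) = 1.329, so the reported rate is 25% below, against 24% without leavers. At D = 104 and 156 the figures are 14% and 10%, against 13% and 9%. If only the leavers have a raised rate (5 times, d = 10%), D = 52 gives (3 + 46.8) / 47.4 = 1.051, about 5% below; D = 104 gives about 2.5%.

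**Step 5: the Week 0–2 interval.** If no form is taken at Week 2, the Week 4 form read literally covers only Weeks 2–4. Weeks 0–2 then carry 15 − 1 = 14 days of time with no recorded use. That is 14 of the 57 − 1 = 56 days before Week 8, or 25%. The inactive stratum, timed from Baseline, already has this problem.

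**The case against.** The strongest reply is that the rate is coherent. Numerator and denominator both start at Week 8, and Week 8 is the start that protocol 8.1.4 declares for active entrants. SAP 10.1 itself recognises variables defined differently by entry stratum. Weeks 0–8 also mix a carried-over flare with study treatment, since protocol 5.6.4 gives no loading dose and some entrants come from placebo. A post-Week-8 rate is a legitimate quantity. That stands, and it is a reason to keep the rate, but not a reason to report it alone and without saying what it is conditional on.

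Second, the direction is not known. The HRU counts visits beyond the protocol-required ones. Scheduled visits at Weeks 2, 4 and 8 could absorb flare care that later, with 12-week gaps, would become unscheduled visits. R may be near or below 1. This also stands.

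Third, early leavers add only about one percentage point in Step 4; the rest of any difference comes from the assumed R. This is correct.

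Fourth, early failures appear elsewhere: discontinuation by reason (SAP 8.0), flare with or without discontinuation and quiescence with non-responder imputation (SAP 10.2), and hospital admissions as serious adverse events. None of these shows utilisation in Weeks 0–8.

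Fifth, simply moving the start to Baseline brings in the Week 0–2 gap of Step 5, which the present Week 8/Week 12 pairing avoids. The change therefore has to settle that too.

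**Conclusion.** Four points need no assumption. Collected Week 0–8 utilisation is never reported for active entrants. The rate is conditional on remaining past Week 8, and the SAP does not say so. The time rule is undefined or negative for those who leave before Week 8. The two strata have different time origins, so their rates are not comparable. SAP 10.3 is also out of line with the current SAP 10.1.

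A reader might go further and infer that the rate understates the uveitis care burden, or that active entrants are made to look closer to inactive ones than they are. The documents do not support that as a finding. It requires R above 1, and they give no utilisation rates and no early-exit share. Under assumed values the understatement is about 7–13% at R = 2 and 13–24% at R = 3 for mean follow-up of 104 down to 52 weeks. It shrinks with longer follow-up, is nil at R = 1, and reverses below 1.

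Severity is low. HRU is listed among the other variables of a descriptive study whose primary objective is safety, and no comparison of HRU between strata is planned.

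**What to change.** In SAP 10.3:

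- Report active-entry HRU from Baseline, split into Weeks 0–8 and after Week 8. The second row is the rate now planned.
- State that a subject with no Week 8 date, or whose last HRU precedes Week 8, contributes only to the first row and never negative time.
- Report how many active entrants contribute no time after Week 8.
- Reconcile 10.3 with 10.1, and label any rate that starts at Week 8 as such.
- Settle the Week 2 form. Table 1 shows none, protocol 5.3.1.1 says all visits, and SAP 10.3 counts from Week 2. State whether the first post-baseline form covers Weeks 0–2, and match person-time to the recall period in both strata.

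The cost is SAP wording and one more derivation; no new data are needed. The downside is a possibly less favourable active-entry rate.
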